8.6.1.1 Multiplicity

In order to control for [REDACTED] the [REDACTED] will be used in the determination of dose level success against placebo. There are [REDACTED] for the primary endpoint ACR20: [REDACTED]

[REDACTED]. The [REDACTED] from [REDACTED] the four comparisons above are ordered from lowest to highest value. The first p-value [REDACTED] the sequence will be compared with [REDACTED] the second lowest will be compared with [REDACTED] the third lowest will be compared with [REDACTED] and the highest will be compared with [REDACTED]. If any p-value is less than the specified value, the corresponding test is declared significant. This test procedure will protect [REDACTED] at the [REDACTED] level.

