8 STATISTICAL METHODS

8.1 General Statistical Conventions

All statistical procedures will be completed using SAS version 9.4 or higher.

Unless otherwise stated, all statistical testing will be two-sided and will be performed using a significance (alpha) level of 0.05.

Continuous variables will be summarized using descriptive statistics, including number of subjects (n), mean, median, standard deviation (SD), minimum and maximum. One additional decimal point for mean and median and [REDACTED] for SD will be used.

For categorical variables, summaries will include counts of subjects and percentages. [REDACTED]

For summary purposes, baseline will be defined as the last available value prior to the date of first IMP administration; all summaries will be presented by treatment group, unless otherwise specified.

For reporting purpose, summary tables for efficacy variables and safety variables will be displayed by nominal visit as appropriate. Unscheduled assessments will not be included in the summary tables, but will be in data listings.

All subject data, including those derived, will be presented in individual subject data listings. Unless otherwise stated, unscheduled visit results will be included in date/time chronological order, within patient listings only. All listings will be sorted by treatment group, subject number, date/time and visit. The treatment group as well as patient's sex and age will be stated on each listing. Unless otherwise stated, data listings will be based on all randomized subjects.

The treatment groups will be displayed in the format below in tables including [REDACTED]:

- [REDACTED]
- [REDACTED]
- [REDACTED]
- [REDACTED]
- [REDACTED]

The treatment groups will be displayed in the format below for tables including [REDACTED] and all listings:

Statistical Analysis Plan (SAP)

- [REDACTED]
- [REDACTED]
- [REDACTED]
- [REDACTED]
- [REDACTED]

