8.6.2 Analysis of primary efficacy endpoint(s)

The primary efficacy variable is ACR20 at [REDACTED] ACR20 will be analysed with [REDACTED] as described in [REDACTED] Early withdrawals and any other subjects with ACR20 undeterminable [REDACTED] will be classified as [REDACTED]. Subjects who fail to show minimal response to treatment [REDACTED]

[REDACTED] may have their background medications adjusted according to the maximum permitted daily dose described in the protocol and continue in the study. Any subject requiring these adjustments will be counted as a non-responder for the primary analysis.

The primary efficacy analysis will be carried out using the subjects from the FAS. To control for [REDACTED], the [REDACTED] will be used. The pair-wise comparisons for the primary endpoints [REDACTED]

[REDACTED]
[REDACTED]

Statistical Analysis Plan (SAP)

Subgroup analysis will be performed for each of the following subgroup variables:

- Prior anti-TNF use [REDACTED]
- Baseline weight [REDACTED]

Estimates of the difference between the treatment groups, along with the [redacted] CI ([redacted]), will be presented for each defined category of each subgroup variable.

If sample size for a category of a subgroup factor is too small, the analysis for that subgroup may not be performed.

The primary purpose of the subgroup analyses is to check for consistency of results across stratification factors.

A sensitivity analysis of ACR20 with ESR replacing CRP will be performed.

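### The multiplicity decision sentence judges each ranked p-value alone; if the redacted values rise with rank, it matches neither a step-up nor a step-down procedure

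*SAP*

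**What the plan says.** Section 8.6.1.1 introduces a procedure, its name redacted, that "will be used in the determination of dose level success against placebo". The p-values from "the four comparisons above are ordered from lowest to highest value". Each rank then has its own comparison value: after the first p-value, "the second lowest will be compared with [REDACTED] the third lowest will be compared with [REDACTED] and the highest will be compared with" a further value. All four values are redacted. The decision sentence that follows is complete and readable: "If any p-value is less than the specified value, the corresponding test is declared significant". The next sentence says that this procedure protects an error rate, but the rate and its level are redacted.

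Section 8.6.2 refers to the procedure again with its name redacted. The text after "The pair-wise comparisons for the primary endpoints" is redacted up to the subgroup paragraph. Section 8.1 sets the general convention, unless otherwise stated: "all statistical testing will be two-sided and will be performed using a significance (alpha) level of 0.05".

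**The concern.** The words any and corresponding test make each rank a decision of its own. A stepwise procedure links the ranks in one of two ways:

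- **Step-up** starts at the highest p-value. Once one is below its value, that test and every test with a smaller p-value succeed.
- **Step-down** starts at the lowest p-value. At the first that is not below its value, that test and every test with a larger p-value fail.

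The readable sentence contains neither link. With values that rise with rank, a p-value can miss the strict value at a low rank while a larger one meets the looser value at a higher rank. The sentence would then declare the dose with weaker evidence successful and the dose with stronger evidence not.

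This rule decides which doses succeed on the primary endpoint. Section 1 says that the SAP supersedes the protocol's statistical considerations, so its wording governs.

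**Working it through.** The plan shows no readable figure to reproduce. The check applies three rules to the same p-values: the sentence as the whole rule, step-up, and step-down.

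**Inputs from the SAP**
- Four comparisons (8.6.1.1), each active arm against placebo (8.6.1), with five treatments (3.3).
- Two-sided testing at 0.05 (8.1). The level in 8.6.1.1 itself is redacted.

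**Assumptions**
- Values by rank: 0.05/4 = 0.0125, 0.05/3 = 0.0167, 0.05/2 = 0.025, and 0.05. Alternatives: i × 0.05/4 (0.0125, 0.025, 0.0375, 0.05), and 0.0125 at every rank.
- Four z-statistics with pairwise correlation 0.5, as for equal arms sharing one placebo group; 0.3 and 0.7 as the range.
- Effects expressed as noncentrality, that is, the true difference in standard errors.

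**Worked example**, p = 0.020, 0.022, 0.024, 0.030:

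| Rank | p | Value | Below? | Sentence | Step-up | Step-down |
|---|---|---|---|---|---|---|
| 1 | 0.020 | 0.0125 | no | fail | pass | fail |
| 2 | 0.022 | 0.0167 | no | fail | pass | fail |
| 3 | 0.024 | 0.025 | yes | pass | pass | fail |
| 4 | 0.030 | 0.05 | yes | pass | pass | fail |

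The sentence passes only the two largest p-values, step-up passes four, and step-down passes none.

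**How the rules relate.** The sentence passes everything that step-down passes and nothing that step-up does not. It differs from both exactly when some rank fails and a higher rank passes, which is a reversal.

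**Share of trials with a reversal** (correlation 0.5, values 0.05/4 to 0.05):

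| Noncentralities of the four doses | Reversal |
|---|---|
| 2.0 / 2.5 / 2.8, equal in all four | 3.5% / 3.9% / 3.5% |
| 1.5, 2, 2.5, 3 | 2.6% |
| 0, 2.5, 2.5, 2.5 | 1.1% |
| 0, 0, 2.5, 3 | 0.3% |
| 0, 0, 0, 0 | 0.1% |

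Over correlations 0.3 to 0.7 the range is 0.04% to 4.5%. With i × 0.05/4 and four equal effects of 2 to 3, it is about 2.0% to 3.7%. With 0.0125 at every rank it is 0%.

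**Operating characteristics** (four equal effects at 2.5, correlation 0.5, values 0.05/4 to 0.05):

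| | Sentence | Step-up | Step-down |
|---|---|---|---|
| At least one dose succeeds | 80.8% | 80.8% | 80.1% |
| All four succeed | 38.7% | 41.7% | 38.7% |
| Mean number of successes | 2.39 | 2.44 | 2.35 |

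**Family-wise error** (1,000,000 simulated trials per scenario, same values):

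| Noncentralities | Sentence | Step-up | Step-down |
|---|---|---|---|
| 0, 0, 0, 0 | 0.044 | 0.044 | 0.043 |
| 0, 0, 4, 4 | 0.044 | 0.045 | 0.042 |
| 0, 4, 4, 4 | 0.044 | 0.045 | 0.043 |

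With i × 0.05/4 and noncentralities 0, 0, 3, 3, all three rules slightly exceed 0.05 (about 0.054, 0.055 and 0.052). That excess comes from the values, since both stepwise rules show it too.

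**The case against.** The strongest objection is that the deciding text is redacted: the procedure name, all four values, words inside the ordering text, and most of the corresponding paragraph in 8.6.2. A stepping direction could stand in any of these places, and redacted text is not missing text. Under step-up the sentence states nothing false, and nothing readable shows that step-down is used. The sentence can also be read as shorthand within a named procedure, and a programmer who follows that procedure would not be misled. Every magnitude rests on assumed values, effects and correlation, and even then the differences are small.

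Much of this stands. The premise of rising values cannot be confirmed, and equal values would remove the problem. No contradiction is demonstrated; it arises only under step-down. What remains is that the decision sentence is itself fully readable and treats each rank alone. If hidden text says step-down, the sentence conflicts with it. If hidden text says step-up, the sentence understates which tests succeed. Ranking the p-values and stating a value for each rank would serve little purpose if all the values were equal.

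**Conclusion.** The concern holds in conditional form: if the values rise with rank, the stated decision rule is neither step-up nor step-down, and followed literally it can reverse the order of dose conclusions on the primary endpoint. Under the assumptions used, this affects at most a few percent of trials. Relative to step-up, the cost is lost successes (all four doses in 38.7% rather than 41.7% of trials at noncentrality 2.5). Relative to step-down, it adds successes that the procedure would not allow. No claim of type I error inflation is made. The point is minor, and confidence is low because the procedure and its values are redacted.

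**What to change.** Before unblinding, replace the decision sentence in 8.6.1.1 with one that matches the named procedure:

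- *If step-up:* Start with the highest p-value. Once a p-value is below its value, that test and all tests with smaller p-values are declared significant.
- *If step-down:* Start with the lowest p-value and stop at the first that is not below its value; that test and all tests with larger p-values are not significant.

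No preference between the two is expressed, because the procedure cannot be identified from the readable text. If the redacted text already states the direction, only this sentence needs aligning with it. If all four values are equal, no change is needed. The cost is one SAP sentence and no new data.

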8.6.2 Analysis of primary efficacy endpoint(s)

The primary efficacy variable is ACR20 at [REDACTED] ACR20 will be analysed with [REDACTED] as described in [REDACTED] Early withdrawals and any other subjects with ACR20 undeterminable [REDACTED] will be classified as [REDACTED]. Subjects who fail to show minimal response to treatment [REDACTED]

[REDACTED] may have their background medications adjusted according to the maximum permitted daily dose described in the protocol and continue in the study. Any subject requiring these adjustments will be counted as a non-responder for the primary analysis.

The primary efficacy analysis will be carried out using the subjects from the FAS. To control for [REDACTED], the [REDACTED] will be used. The pair-wise comparisons for the primary endpoints [REDACTED]

[REDACTED]
[REDACTED]

Statistical Analysis Plan (SAP)

Subgroup analysis will be performed for each of the following subgroup variables:

- Prior anti-TNF use [REDACTED]
- Baseline weight [REDACTED]

Estimates of the difference between the treatment groups, along with the [redacted] CI ([redacted]), will be presented for each defined category of each subgroup variable.

If sample size for a category of a subgroup factor is too small, the analysis for that subgroup may not be performed.

The primary purpose of the subgroup analyses is to check for consistency of results across stratification factors.

A sensitivity analysis of ACR20 with ESR replacing CRP will be performed.

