4 STUDY ENDPOINTS

4.1 Primary efficacy endpoint

The primary efficacy endpoint is the proportion of subjects who achieve ACR20 at Week 24.

The ACR20 is defined as at least a [REDACTED] and [REDACTED]: 1) the Physician Global Assessment (PGA) of disease activity (as measured using a VAS), 2) the Patient Global Assessment (PtGA) of disease activity (as measured using a VAS), 3) patient pain assessment (as measured using a VAS), 4) patient self-assessed disability (as measured using the HAQ-DI), and 5) acute-phase CRP¹.

The components of the ACR assessments that will be used in this study are:

- Tender joint counts [REDACTED]
- Swollen joint counts [REDACTED]
- PGA of disease activity [REDACTED]
- PtGA of disease activity [REDACTED]
- Patient's pain assessment [REDACTED]
- Patient's self-assessed disability (HAQ-DI)
- Acute-phase hsCRP

If the value in any of the components at a time point is missing, the component variables that are not missing will be used to determine the response status. As a general principle, if there are sufficient non-missing components to determine whether the ACR endpoint is a response or non-response, then ACR endpoint is not missing, else if the available non-missing components are not sufficient to determine the response status of ACR endpoint then it is considered missing.

If the baseline value of any component is [REDACTED], the following algorithm will be used in evaluating the percent change from baseline:

- If change from baseline is also [REDACTED] then percent change from baseline is set to be [REDACTED]
- If change from baseline is [REDACTED], then percent change from baseline is set to be [REDACTED]

These percentages will be used to derive the ACR endpoints.

In addition, any CRP value below the LLOQ will be reported as [REDACTED] in database and will be [REDACTED] and used in analyses.

Another version of ACR20 will be derived with ESR replacing hsCRP.

Statistical Analysis Plan (SAP)

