6.2 Per Protocol Analysis Set (PPAS)

The PPAS will include all subjects in the FAS without any major protocol deviations that could have influenced the validity of the data for the primary efficacy endpoint. The deviations can include but are not limited to:

- Key inclusion/exclusion criteria not satisfied
- Presence of relevant protocol deviations with respect to factors likely to affect the efficacy of treatment where the nature of protocol deviations will be defined before breaking the blind
- Rescue medication use
- Inadequate study medication compliance which will be determined before breaking the blind

Major protocol deviations to be excluded from the PPAS will be finalized and documented in a memo prior to the lock and unblinding of the database.

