6.6 Protocol deviations/violations and exclusions from analysis sets

All violations and exclusions of subjects from analysis sets will be identified at the Classification

Statistical Analysis Plan (SAP)

Meeting just prior to study unblinding, through clinical review input provided by Sponsor, using the following sources of information:

- Supportive subject listings, provided by the [REDACTED] ahead of the Classification Meeting, based on data recorded on the eCRF.
- Protocol Deviation Logs, provided by [REDACTED].

Further, deviations from protocol will be classified as major/minor or key/non-key depending on what is available in [REDACTED].

The protocol deviations that will lead to subject exclusion from the PPAS are listed as below. It is possible that unexpected deviations will arise as the study moves forward. Therefore, more deviation categories may be added to the list later. Prior to database lock, a classification meeting will be conducted to identify subjects to be excluded from PPAS, and the decision will be documented in a separate file.

- Subject without a diagnosis of PsA by the Classification of Psoriatic Arthritis (CASPAR) criteria with symptoms present for at least 6 months
- [REDACTED]
- Non-compliance with study treatment [REDACTED]
- Disallowed concomitant medications
- [REDACTED]
- [REDACTED]

Statistical Analysis Plan (SAP)

7

STATISTICAL CONSIDERATIONS AND ANALYSIS

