7.2 Handling of missing data and outliers

7.2.1 Missing data analysis methods

In the primary analysis, ACR20 response rate at [REDACTED], missing values will be handled by setting the ACR20 value to nonresponsive. This approach will be used for all [REDACTED] endpoints (ACR20, ACR50, ACR70, DAS28-CRP, PASI75/90/100, and MDA) at all time points.

For a composite [REDACTED] endpoint (such as ACR20), if the values for any of the components at a time point are missing, the non-missing component variables will be used to determine the response status. If the response status cannot be determined due to missing components, then the composite response-type endpoint status is considered [REDACTED] for that time point.

For the HAQ-DI, LDI, LEI, SF-36 and PsAID instruments, rules suggested by the developers of these will be followed in calculating scores when individual question/items may be missing.

Details on handling missing data are outlined in [REDACTED].

In general, missing values for any of the endpoints will not be imputed when summarizing these endpoints using descriptive statistics.

In addition, missing values for safety endpoints will not be imputed.

Statistical Analysis Plan (SAP)

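### As far as section 8.6.2 can be read, the primary non-responder rule covers permitted background adjustments but not rescue or disallowed PsA therapy before Week 24

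*SAP*

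**What the plan says.** Section 4.1 sets the endpoint: "The primary efficacy endpoint is the proportion of subjects who achieve ACR20 at Week 24". Section 8.6.2 sets the analysis set: "The primary efficacy analysis will be carried out using the subjects from the FAS". Section 6.1 defines the FAS by randomization and dosing, and readably excludes nobody for other therapy.

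The readable text gives three routes to non-response at Week 24:

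- **Withdrawal or undeterminable status.** Section 8.6.2 assigns a class to "Early withdrawals and any other subjects with ACR20 undeterminable". The class itself is blacked out there.
- **Missing ACR20.** Section 7.2.1: "missing values will be handled by setting the ACR20 value to nonresponsive".
- **Permitted background adjustment.** Section 8.6.2 says that subjects without minimal response "may have their background medications adjusted according to the maximum permitted daily dose described in the protocol and continue in the study". The next sentence is "Any subject requiring these adjustments will be counted as a non-responder for the primary analysis".

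Other therapy appears in the definition of the per-protocol set. Section 6.2 lists "Rescue medication use" among deviations that could affect the validity of the primary endpoint data, and section 6.6 lists "Disallowed concomitant medications" among the grounds for leaving the PPAS.

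**The concern.** The plan already takes the view that a subject who needed extra background treatment should not be credited with a response. The sentence that does this is tied to one kind of change, the one made within the permitted ceiling. A change outside the rules confounds ACR20 at least as much, yet no readable sentence gives it a response status. A capped, permitted change is therefore a failure, while a prohibited one can be a success.

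At stake is the meaning of the primary response rate. Some responses may be due to therapy other than the randomized treatment, and if arms differ in how often that happens, the treatment difference shifts. Section 8.6.3 applies the ACR20 methods to the secondary response-type endpoints, so the gap may carry over to them.

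**Working it through.** The point concerns a rule. The readable SAP shows no sample size, response rate or frequency of disallowed therapy, so there is no planned figure to reproduce.

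**Step 1: follow one subject through the rules.** Take a subject in the FAS who starts a disallowed PsA therapy before Week 24, remains in the study and has enough ACR components at Week 24.

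| Rule | Does it apply? |
|---|---|
| Early withdrawal (8.6.2) | No, the subject remains |
| Undeterminable or missing ACR20 (8.6.2, 7.2.1) | No, section 4.1 derives a status from the available components |
| Permitted background adjustment (8.6.2) | No, the therapy is outside that permission |
| FAS exclusion (6.1) | None readable |
| PPAS exclusion (6.2, 6.6) | Yes, but the primary analysis uses the FAS |

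The observed ACR20 stands. The one readable sensitivity analysis of the primary endpoint replaces CRP with ESR and does not bear on this.

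**Step 2: size of the effect.** Let f be the share of an arm that uses such therapy and has a determinable Week 24 ACR20, and q the share of those users who meet ACR20, taken as equal across arms. Compared with counting users as non-responders, the rule as written:

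- raises an arm's response rate by f × q;
- changes the active-minus-placebo difference by q × (f_active − f_placebo), for each active arm against placebo.

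All values of f and q below are assumptions.

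| Use, placebo vs active | q = 40% | q = 80% |
|---|---|---|
| 5% vs 2% | 0.40 × (−0.03) = −1.2 points | 0.80 × (−0.03) = −2.4 points |
| 10% vs 3% | 0.40 × (−0.07) = −2.8 points | 0.80 × (−0.07) = −5.6 points |
| 5% vs 5% | 0 | 0 |
| 2% vs 5% | 0.40 × 0.03 = +1.2 points | 0.80 × 0.03 = +2.4 points |

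A negative sign means that the rule as written gives a smaller difference than the extended rule.

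**The case against.** **Blacked-out text and the protocol.** Parts of 8.6.2, the cross-reference for missing data in 7.2.1, the derived-variable table in 7.1 and section 10 cannot be read. A rule could sit in any of them, and the protocol may require subjects on prohibited therapy to stop. Section 3.1 has subjects without sufficient benefit discontinued from study drug so that they may receive other treatment, although the period is blacked out. This stands as a limit: the affected group may be small, and the SAP gives no frequency. It does not remove the point. The rule sentence in 8.6.2 is complete and narrow, section 3.1 does not say that disallowed therapy makes a subject an early withdrawal, and it still requires an assessment after study drug stops.

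**A legitimate estimand.** Keeping protocol violators with observed outcomes while counting planned escape as failure is a recognised approach. But the readable SAP does not present it as a choice, and sections 6.2 and 6.6 show that it regards these medications as relevant to the primary endpoint.

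**Stronger readings that the documents do not support.** A reader might infer that the gap necessarily dilutes the treatment effect. More use on placebo is a plausible expectation, but the SAP does not document it, and the sign follows whichever arm uses more.

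A reader might also infer that excluding rescue users from the PPAS distorts a robustness check. No readable sentence runs an efficacy analysis on the PPAS, and such exclusions are ordinary for a per-protocol set. The direction is not fixed either. Assume true rates of 50% vs 75% and use in 20% of placebo and 8% of active subjects:

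- If no user responds, exclusion gives 0.50/0.80 = 62.5% and 0.75/0.92 = 81.5%, so 25 points become 19.0.
- If 40% of users respond, it gives (0.50 − 0.08)/0.80 = 52.5% and (0.75 − 0.032)/0.92 = 78.0%, a difference of 25.5 points.
- If 80% respond, it gives (0.50 − 0.16)/0.80 = 42.5% and (0.75 − 0.064)/0.92 = 74.6%, a difference of 32.1 points.

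The loss disappears or reverses, so section 6.2 needs no change on this account.

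**Conclusion.** The point holds in a limited, conditional form. In the readable text, treatment-related non-response covers permitted background adjustments only, and a subject on disallowed PsA therapy with a determinable Week 24 ACR20 keeps the observed result in the FAS. With 5% use on placebo, 2% on active and 40% to 80% of users responding, the primary difference shrinks by 1.2 to 2.4 points. Equal use, with equal q, gives no shift, and higher active use widens the difference. These rates are assumptions, and the conclusion is subject to the blacked-out text and the protocol. Because the sign depends on which arm uses more, the rule should be settled before treatment codes are known.

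**What to change.** In section 8.6.2, replace the sentence on adjustments with a rule of this kind: any subject who, before the Week 24 assessment, has background PsA therapy adjusted, or starts rescue or disallowed therapy that can affect ACR20, counts as a non-responder for response-type endpoints from that date.

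Staff blinded to treatment should classify the qualifying medications. The Classification Meeting in section 6.6 already reviews these deviations, but it is held just before study unblinding, while section 3.2.2 foresees unblinding some personnel for the interim analysis. The classification should therefore be fixed before anyone is unblinded, including for that analysis.

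If blacked-out text or the protocol already contains such a rule, a cross-reference in 8.6.2 is enough.

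The cost is SAP wording and an earlier timing of a blinded review that is already planned. The downside is a slight fall in response rates in each arm where such therapy is used, by f × q: for example, 0.05 × 0.40 = 2.0 to 0.05 × 0.80 = 4.0 points at an assumed 5% use.
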